7.2. Study Procedures

7.2.1. Visit 1

Study procedure is completed over the course of one day as described above in study design.

7.3. Duration of Participation

Duration is time from consent signing until patient is medically ready for discharge.

7.4. Test Article(s) (Study Drug(s) and/or Study Device(s))

7.4.1.Description

160mg of 1% lidocaine is approved by the FDA for anesthetizing tracheobronchial tree. The mode of administration (spray as you go vs nebulized vs atomized) has been shown to have similar safety profile however efficacy has not been determined.

7.4.2. Treatment Regimen

Their airways will be anesthetized using 160mg of lidocaine, administered by one of the following techniques:

- 1. "Spray as you go" 16mL of 1% lidocaine sprayed in 4 mL aliquots. One at the vocal cords, one at midtrachea, one at left main stem bronchus and one at right mainstream bronchus.
- 2. Jet Nebulizer 8 mL of 2 % lidocaine administered via a jet nebulizer over ten minutes, followed by procedure immediately after.
- 3. Vibrating Mesh Nebulizer 8 mL of 2 % lidocaine administered via a vibrating mesh nebulizer over ten minutes, followed by procedure immediately after.

7.4.3. Method for Assigning Subject to Treatment Groups

Subject forms will have administration mode documented and will be placed in sealed envelopes. Immediately prior to procedure, envelope will be opened to determine which mode of lidocaine administration will be performed. [name] will secure all envelopes within locked cabinet in [name]'s office. Subject will be told of their assigned treatment group. Inpatient/Outpatient will be a 50/50% stratification.

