1.3. Secondary Study Endpoints

Secondary endpoints will include: additional amount(s) of fentanyl and propofol used to suppress cough during procedure, cough and sore throat post-procedure and time to emergence following the end of the procedure.

2. Background

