2.3. Study Rationale

While the procedures of flexible bronchoscopy and endobronchial ultrasound is commonly performed to assess a wide range of lung disease, studies evaluating the mode of administration of topical lidocaine to prevent coughing and improve efficiency of the procedure have not yet been completed. We propose a prospective, randomized, stratified sampling, open label study of topical vs nebulized vs atomized lidocaine during flexible bronchoscopy and endobronchial ultrasound. Postoperative outcome assessors will be blinded to intraoperative therapy. We propose to evaluate the different modes of administration of topical lidocaine and their effect on the number of severe coughs as per anesthesia and the bronchoscopist, total dosing of anesthesia, post-procedure cough and sore throat and complications related to lidocaine.

As there have been no studies in regards to the mode of lidocaine application in bronchoscopy, our study is a feasability study to identify if a difference is present between nebulized and topical groups. If one is identified, we will plan to determine number needed to power a future superiority study.

Inclusion and Exclusion Criteria

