- 2. Nebulizer 2 % (preservative free) lidocaine (dose 2mg/kg max dose 160 mg) will be administered via a jet nebulizer, in the operating room over ten minutes, followed by procedure immediately after. The patient will be sitting propped up and his SpO2, EKG and BP will be monitored during this time. The jet nebulizer supply tube will be connected to central oxygen at 6 L/min and the duration of nebulization will be dryness of the nebulizing chamber or max of 10 minutes. [The Salter Series Small Volume Jet Nebulizer will be used.]
- 3. Vibrating Mesh Nebulizer 2 % (preservative free) lidocaine (dose 2mg/kg max dose 160 mg) will be administered via a vibrating mesh nebulizer, in the operating room over ten minutes, followed by procedure immediately after. The patient will be sitting propped up and his SpO2, EKG and BP will be monitored during this time. The jet nebulizer will be

connected to central oxygen at 6 L/min and the duration of nebulization will be dryness of the nebulizing chamber or max of 10 minutes. [The Aerogen Solo Vibrating Mesh Nebulizer will be used.]

Patient will undergo scheduled procedure of flexible bronchoscopy or endobronchial ultrasound examination. During procedure, bronchoscopist and anesthesiologist will count the number of episodes of cough. Cough is defined as a cough which requires intervention such as additional dose of anesthetic or requires a pause in the procedure. During procedure, BIS monitor average, number of vasopressor interventions for MAP <60, induction time, procedure time and wake up time will be documented in the research record.

Following procedure, patient will be brought to post-op anesthesia care unit. Time to discharge readiness will be collected as well as the responses of the patient to the following questions:

- sore throat: absent, mild, moderate, severe
- cough: absent, mild, moderate, severe

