7.4.6.3. Preparation and Dispensing

Mode of administration will be determined day of procedure by selection of randomized, sealed envelopes containing subject form with administration mode. The atomized and nebulized lidocaine will be prepared and administered by the anesthesiologist. The "spray as you go" lidocaine will be prepared by the scrub nurse and administered by the bronchoscopist. Preparation involves loading medication into administration devices.

Medication will not be dispensed directly to subject.

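### Post-procedure cough and sore throat are the patient's own ratings, and 7.4.3 lets the patient learn the arm before giving them, so the blinded-assessor statement in 2.3 does not cover these two secondary endpoints

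*Combined protocol and SAP*

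**What the plan says.** Section 2.3 describes the trial as an "open label study of topical vs nebulized vs atomized lidocaine during flexible bronchoscopy and endobronchial ultrasound" and adds one safeguard: "Postoperative outcome assessors will be blinded to intraoperative therapy". Section 1.3 lists "cough and sore throat post-procedure" among the secondary endpoints.

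Section 7.1 sets out how these are obtained in the recovery unit: "Time to discharge readiness will be collected as well as the responses of the patient to the following questions". The two questions are sore throat and cough, each answered as absent, mild, moderate or severe.

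On allocation, 7.4.3 states "Immediately prior to procedure, envelope will be opened to determine which mode of lidocaine administration will be performed", and later in the same paragraph "Subject will be told of their assigned treatment group". Section 7.4.5 names only the anesthesiologist and bronchoscopist as not blinded, and 19.6 says that the modes of administration are not blinded. No section keeps the patient unaware of the technique until the recovery questions have been answered.

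**The concern.** For these two endpoints the rater is the patient; staff only ask and record. Masking the person who asks removes one source of bias, the way the question is put and written down. It cannot remove the other, the patient's own expectation about the technique received. Four-level ratings of cough and throat discomfort are subjective and open to that influence.

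Two things are at stake. First, a reader of 2.3 may take all the postoperative outcomes to be blinded and report them so. Second, the analysis is descriptive (8.3), so a difference in ratings that came from expectation would look the same as one that came from technique. Section 2.3 says that an observed difference between nebulized and topical groups would lead to planning a superiority study.

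**Working it through.** No figure in the plan bears on this point: 8.2 marks sample size determination as not applicable and 8.3 plans medians, interquartile ranges and percentages. The check is a cross-reading.

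1. **Are these endpoints?** Yes. Section 1.3 lists both as secondary.

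2. **Who rates them?** The patient. Section 7.1 records patient responses, and 16.1 places the collection in the post-anesthesia care unit.

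3. **When is the allocation known to staff?** Just before the procedure, when the envelope is opened (7.4.3), and so before any recovery-unit rating.

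4. **When is the patient told?** Section 7.4.3 says that the patient will be told, but not when. The sentence is separate from the one on opening the envelope. Knowledge before the rating is therefore permitted, but not established.

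5. **What does 2.3 cover?** Postoperative assessors. This applies to the person who puts the questions and to any item that staff judge, such as time to discharge readiness, which is collected but is not a listed endpoint. It does not reach an answer that the patient supplies.

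6. **Is the primary endpoint touched?** No. Severe intraoperative coughs are identified by the anesthesiologist and bronchoscopist (1.2), so what the patient is told does not enter into it.

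7. **Could deferred disclosure keep patients unaware?** That depends on the order of events in 7.1, which reads two ways. The text describes induction, then the laryngeal mask, then lidocaine by the assigned technique. The two nebuliser items describe a patient seated upright and monitored during up to ten minutes of nebulisation, with the procedure straight after; this may mean that the patient is awake.
   - If every patient is anaesthetised before lidocaine is given, deferral could keep patients unaware in all three arms.
   - If nebuliser patients are awake, and assuming that patients have been told what the techniques are, a patient can tell spray from nebuliser without being informed. Deferral then helps mainly for jet versus mesh.

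**The case against.** The strongest reply is that nothing here is inconsistent. The study is declared open label, 2.3 promises blinded assessors and not blinded patients, and a masked interviewer with an unmasked patient is a coherent design. That stands. A reader might infer that 2.3 and 7.4.3 contradict each other; they do not. The point is only that the safeguard stops short of these two endpoints and that a cheap change would extend it.

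A second reply concerns timing. If the envelope is opened with the patient already anaesthetised, the patient could only be told later, perhaps after rating. That also stands. A reader might infer that every patient rates while knowing the arm, but the text supports only that patients may know.

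Third, a reader might infer that the recovery-unit assessor is unmasked too, because "Subject forms will have administration mode documented and will be placed in sealed envelopes" and 10.2 describes data as collected on subject forms. The documents do not say that recovery staff use or see that form, and section 9 refers data handling to a Research Data Plan Review Form that is not among the documents. A leak by this route is not shown, so a separate collector from outside the procedure room is not called for on this evidence.

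Finally, deferral may not help the nebulized-versus-topical comparison that 2.3 names. That is true if patients are awake during nebulisation. It limits the first part of the fix but not the wording change in 2.3, which is right in either case.

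**Conclusion.** The point holds, as a minor one. As written, patients may know their technique when they rate post-procedure cough and sore throat, and the blinded-assessor statement does not blind those ratings.

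The size of any bias cannot be computed: the documents give no expected distribution of the ratings and nothing on how far expectation might shift them. It is tempting to count the patients or arm comparisons that deferral could reach and to treat the count as a magnitude. Such a count describes the reach of the remedy, not the size of a bias, and the plan specifies no pairwise tests to which it could apply.

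The rating of minor rests on this: two secondary endpoints are involved, the study is a 48-patient feasibility study with descriptive analysis, the primary endpoint is untouched, and no decision rule in the documents turns on these ratings. How much deferral achieves rests on the order of induction and nebulisation, which the protocol leaves unclear.

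**What to change.** 1. **Section 7.4.3:** state that the assigned technique is disclosed to the patient only after the recovery-unit cough and sore-throat questions have been answered. Align the consent wording if needed.
2. **Section 2.3:** limit the blinding statement to the staff assessor, and label post-procedure cough and sore throat as patient-reported.
3. **Section 7.1:** reconcile the passages on the order of induction and nebulisation, so that it is clear which case applies. If patients are awake during nebulisation, describe the two ratings as open-label for spray versus nebuliser; item 1 then helps mainly for jet versus mesh.

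The cost is one sentence each in 7.4.3 and 2.3, and possibly a consent edit. The downside is later disclosure. It still falls on the same day, since 7.2.1 describes a one-day study procedure and the questions are asked in the recovery unit. Items 1 and 2 call for no extra staff.

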7.4.4. Subject Compliance Monitoring

Not required to be monitored as medication is administered by the anesthesiologist or bronchoscopist prior to or during the procedure

7.4.5. Blinding of the Test Article

Mode of administration will not be blinded to anesthesiologist or bronchoscopist.

7.4.6. Receiving, Storage, Dispensing and Return

7.4.6.1. Receipt of Test Article

Lidocaine will be ordered from the pharmacy. The vibrating mesh nebulizer and jet nebulizer will be set up by anesthesiologist and spray as you go will be set up by OR staff and bronchoscopist.

7.4.6.2.Storage

Same medication obtained from pharmacy is used across all three groups, the mode of administration is only part changed and will be completed by anesthesiologist and/or bronchoscopist.

7.4.6.3. Preparation and Dispensing

Mode of administration will be determined day of procedure by selection of randomized, sealed envelopes containing subject form with administration mode. The atomized and nebulized lidocaine will be prepared and administered by the anesthesiologist. The "spray as you go" lidocaine will be prepared by the scrub nurse and administered by the bronchoscopist. Preparation involves loading medication into administration devices.

Medication will not be dispensed directly to subject.

7.4.6.4. Return or Destruction of the Test Article

Not applicable.

7.4.6.5. Prior and Concomitant Therapy

Dextromethorphan syrup 90mg will be given 60 minutes prior to procedure. Post-procedure, subject will be able to use nebulized albuterol. No medications are contraindicated.

8. Subject Numbers and Statistical Plan

8.1. Number of Subjects

48 patients randomly assigned to lidocaine application technique (24 in topical, 12 in jet nebulizer and 12 in vibrating mesh nebulizer). Among each group there will be stratification of flexible bronchoscopy/endobronchial ultrasound procedures and inpatient/outpatient.

8.2. Sample size determination

Not applicable.

8.3. Statistical methods

Descriptive statistics will be used for continuous variables, and presented as medians and interquartile ranges. Categorical variables will be expressed as percentages. The estimated sample size within our institution is 48 patients.

9. Confidentiality, Privacy and Data Management

See Research Data Plan Review Form.

10. Data and Safety Monitoring Plan

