1.1. Study Objectives

The purpose of this feasibility study is to use a multimodal approach of general anesthesia supplemented by topical analgesia during flexible bronchoscopy and endobronchial ultrasound. The aim is to determine if the administration of lidocaine via "spray as you go" vs. nebulizer would result in reduced severity of cough during the procedure and maximizing efficient sample acquisition while limiting the amount of general anesthetic given. The use of the vibrating mesh nebulizer is presumed to lead to an even distribution during lidocaine administration and thereby lead to decreased number of severe coughs during procedure improving efficiency of sample acquisition and reduce the dose of general anesthetic required.

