1.2. Primary Study Endpoints

The primary endpoint will assess if different modes of lidocaine administration ("spray as you go" vs nebulized vs atomized) decrease the severity of intraoperative coughing. Severe coughs will be identified by the anesthesiologist and bronchoscopist as cough which results in pausing procedure and/or requiring repeated dosing of anesthetic.

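### The plan ties sizing of a superiority trial to finding a nebulized-versus-topical difference, but its analysis gives no between-group estimate, interval or criterion

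*Combined protocol and SAP*

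**What the plan says.** Section 2.3 of the combined protocol and SAP gives the purpose: "our study is a feasability study to identify if a difference is present between nebulized and topical groups". It then attaches a consequence: "If one is identified, we will plan to determine number needed to power a future superiority study".

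Section 8.3 is the whole statistical method. For continuous variables: "Descriptive statistics will be used for continuous variables, and presented as medians and interquartile ranges". For the rest: "Categorical variables will be expressed as percentages". It adds only the total of 48 patients. Section 10.7, although headed as statistical tests, repeats the descriptive sentences and names no test. Section 8.2, on sample size, is marked not applicable.

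On what is compared, section 1.1 states the aim as spray versus nebulizer, and section 2.3 has nebulized versus topical. Section 1.1 also carries a presumption about one device: "The use of the vibrating mesh nebulizer is presumed to lead to an even distribution during lidocaine administration". Section 1.2 is wider: "The primary endpoint will assess if different modes of lidocaine administration" reduce cough severity, listing three modes. Section 8.1 allocates "24 in topical, 12 in jet nebulizer and 12 in vibrating mesh nebulizer" and plans strata: "Among each group there will be stratification of flexible bronchoscopy/endobronchial ultrasound procedures and inpatient/outpatient".

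**The concern.** A group median, an interquartile range or a percentage describes one arm. Section 2.3 asks about the difference between arms, and whether a superiority study is sized turns on the answer. Nothing in sections 8.3 or 10.7 turns the arm summaries into a difference, attaches uncertainty to it, or says what would count as having found one.

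Two things are at stake. First, with 48 patients an apparent difference may well be chance, and the planned output would not show whether it is. Second, sizing a trial on cough counts needs the control mean and its dispersion, and section 8.3 reports neither.

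The comparison is also only partly settled. Sections 1.1 and 2.3 agree on spray or topical against nebulizer, and 24:12:12 is compatible with pooling the two nebulizer arms into 24 versus 24. No section says that they will be pooled, and the stated presumption is about the mesh device alone. A choice left until the data are seen could change the conclusion.

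**Working it through.** **The plan's own figure.** 24 + 12 + 12 = 48, which agrees with section 8.3. There is no alpha, power, effect size or event rate, so there is no sample-size calculation to reproduce.

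**Inputs.** Arm sizes are from section 8.1. The endpoint is severe coughs per procedure, from sections 1.2 and 7.1. The rest is assumed: spray-arm mean m between 0.5 and 4, counts ranging from Poisson (1/k = 0) to negative binomial with k = 1, and an observed ratio of 0.50.

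**Step 1: what an observed halving would tell us.**

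SE of the log ratio = sqrt[(1/m + 1/k)/n1 + (1/(0.5m) + 1/k)/n2]; 95% CI = 0.50 × exp(±1.96 × SE).

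- Pooled nebulizers versus spray, m = 0.5, k = 1: SE = sqrt[(2+1)/24 + (4+1)/24] = 0.577, CI 0.16 to 1.55.
- Pooled nebulizers versus spray, m = 4, Poisson: SE = sqrt[0.25/24 + 0.5/24] = 0.177, CI 0.35 to 0.71.
- One nebulizer versus spray (12 versus 24), m = 0.5, k = 1: SE = sqrt[3/24 + 5/12] = 0.736, CI 0.12 to 2.12.
- One nebulizer versus spray, m = 4, Poisson: SE = sqrt[0.25/24 + 0.5/12] = 0.228, CI 0.32 to 0.78.

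The same estimate includes no effect at one end of the assumed range and excludes it at the other. Section 8.3 reports neither the estimate nor the interval.

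**Step 2: does the contrast matter?** If mesh halved cough and jet did nothing, the pooled ratio against spray would be (0.5 + 1.0)/2 = 0.75, against 0.50 for mesh alone.

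**Step 3: can medians and quartiles size a count-based trial?** A Poisson with mean 1.3 and a negative binomial with mean 1.3 and k = 1 both have quartiles 0, 1 and 2. Their variances are 1.3 and 1.3 + 1.3² = 2.99. For 80% power at two-sided 5% to detect a halving:

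n per arm = (1.960 + 0.842)² × [1/m + 1/(0.5m) + 2/k] / (ln 0.5)²

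- Poisson: 7.85 × 2.308 / 0.480 = 37.7, so 38.
- k = 1: 7.85 × 4.308 / 0.480 = 70.4, so 71.

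Identical output under section 8.3 is compatible with either.

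**Step 4: how far would reporting the mean and variance help?** Only partly. In simulated studies, moment estimates from 24 spray patients gave a required n per arm (middle 95%) of about 29 to 65 when the truth was Poisson and about 37 to 133 when k = 1. These ranges overlap, so the dispersion must be carried forward with its uncertainty.

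**The case against.** The strongest reply is that this is a feasibility study, for which descriptive reporting without a powered test is normal. That stands, and neither a test nor a power calculation is asked for here. It does not answer the narrower point, because section 2.3 goes beyond description.

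A reader might infer more than the documents support:

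- *That no comparison is stated anywhere.* Sections 1.1 and 2.3 both give spray or topical versus nebulizer. What is open is whether the two nebulizers are pooled, and which contrast is primary.
- *That section 2.3 is a go/no-go rule.* It conditions only the planning of a sample size.
- *That the information is lost.* The cough counts are collected, so means, variances and contrasts can be computed later. The gap is in pre-specification and reporting.
- *That two observers produce rival counts.* Section 7.1 has the bronchoscopist and anesthesiologist both counting, but section 1.2 can be read as joint identification of severe coughs. A clarifying line would help; it is not a clear defect.

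It is also fair to say that a future trial could be sized on the percentage with any severe cough, which section 8.3's categorical reporting could supply. In the Step 3 example that is 73% versus 57%, so it does separate the two distributions. That weakens the sizing argument, but it leaves the missing estimate, interval and criterion untouched.

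**Conclusion.** The point holds in a limited form. Followed exactly, sections 8.3 and 10.7 cannot answer the question in section 2.3, and the condition placed on the future study has no defined meaning. The fault is one of pre-specification and reporting; it does not invalidate the study or its data.

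Its size cannot be fixed from the documents, because they give no cough rate. Under the assumptions in Step 1, the 95% CI around an observed halving at 24 versus 24 runs from 0.16–1.55 to 0.35–0.71. The 38 and 71 per arm are an example at one assumed mean, not a forecast. This is a cheap improvement that should be made.

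**What to change.** In section 8.3, keep the descriptive summaries and add:

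- **Primary analysis:** the ratio of mean severe coughs per procedure with a 95% CI that allows for overdispersion (for example quasi-Poisson or negative binomial), for one contrast named in advance. Pooled nebulizers versus spray, 24 versus 24, fits sections 1.1, 2.3 and 8.1; the sponsor should confirm it against the mesh presumption in section 1.1.
- **Secondary estimates:** mesh versus spray and jet versus spray, each with a CI.
- **Adjustment:** procedure type and inpatient/outpatient status, the planned strata, are optional if the model is stable.
- **If an arm has no severe cough:** report the difference in the percentage with any severe cough, with an exact or score-type interval. An unequal-variance interval for the difference in means is unsuitable here, because the all-zero arm contributes no estimated variance.
- **Per arm:** mean, variance and percentage with at least one severe cough.

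In section 2.3, replace the condition that a difference be identified with a statement that a future trial will be sized on a clinically important effect, using this study's control rate and dispersion with their uncertainty, which will be wide at this size.

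Section 3.2 excludes patients who receive paralytics, while the contingency plan in section 7.1 provides for rocuronium when cough prevents the procedure. These must be reconciled and the number given rocuronium reported per arm, since leaving these patients out of the analysis could remove the highest counts.

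The cost is SAP wording and a little analysis; the count and both strata are already in the plan. The downsides are a visibly wide interval and possible dilution of a mesh-only effect by pooling.

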10.7. Statistical tests

Descriptive statistics will be used for continuous variables, and presented as medians and interquartile ranges. Categorical variables will be expressed as percentages.

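### The primary outcome is a count of severe coughs, but the plan's only numeric summary is median and IQR, which can hide a halved cough rate if counts are low

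*Combined protocol and SAP*

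**What the plan says.** Section 1.2 builds the primary endpoint on severe coughs: "Severe coughs will be identified by the anesthesiologist and bronchoscopist as cough which results in pausing procedure and/or requiring repeated dosing of anesthetic". Section 2.3 describes the outcome as the "effect on the number of severe coughs as per anesthesia and the bronchoscopist", and section 7.1 says how it is recorded: "bronchoscopist and anesthesiologist will count the number of episodes of cough". The measurement is therefore a whole number per patient.

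Section 8.3 covers numeric data in one sentence, "Descriptive statistics will be used for continuous variables, and presented as medians and interquartile ranges", and section 10.7 repeats it ("presented as medians and interquartile ranges"). The other rule is "Categorical variables will be expressed as percentages". Neither section says whether the cough count counts as continuous or categorical. Neither names a mean, a between-arm contrast, a test or a confidence interval.

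Section 2.3 gives these summaries their purpose: "our study is a feasability study to identify if a difference is present between nebulized and topical groups". If a difference is found, "we will plan to determine number needed to power a future superiority study". Section 8.1 sets the arms at 24 spray, 12 jet nebulizer and 12 vibrating mesh nebulizer. No expected cough rate appears anywhere.

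**The concern.** Only coughs that force an intervention are counted. Patients are under propofol anesthesia with an opioid infusion and have had dextromethorphan beforehand (section 7.1). Zeros and small whole numbers are therefore plausible.

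The median of such data moves only in whole or half steps and ignores how many episodes lie above it. If more than half of each arm has no severe cough, every median is 0, whatever the difference in rates. Adding a difference in medians with an interval would not help, because that difference would also sit at 0.

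The cost falls on the next trial. Two arms with the same median may be read as alike when the total number of coughs differs twofold. Medians and quartiles also do not directly supply the mean and dispersion needed to size a superiority trial on a count.

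**Working it through.** **The plan's own figure.** The only planning number is the total, 24 + 12 + 12 = 48, which adds up. Section 8.2 gives no sample size basis, so there is no rate, effect, alpha or power to reproduce.

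**Inputs.** From section 8.1: spray n = 24; nebulized n = 12 for one device, or 12 + 12 = 24 with the two devices pooled. Assumed, because the documents are silent: a spray mean of 0.5 to 3 severe coughs per patient, a nebulized mean of half that, and counts that are Poisson or negative binomial (NB) with size k = 1 or 0.5 (smaller k means more overdispersion).

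**Step 1: the population medians.** For a Poisson mean m, P(0) = exp(−m) and P(0 or 1) = (1 + m)·exp(−m).
- 0.5 halved to 0.25: P(0) = 0.61 and 0.78. Both medians are 0.
- 1.5 halved to 0.75: P(0) = 0.22 and 0.47; P(0 or 1) = 0.56 and 0.83. Both medians are 1.
- 1.0 halved to 0.5: P(0) = 0.37 and 0.61. The medians are 1 and 0, so they differ.

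In the first two cases the true medians are equal although the rate is halved, so more patients would not remove the tie. In the third the median does its job.

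**Step 2: simulated trials, 24 v 24, rate halved.** Each cell reads Poisson / NB k = 1 / NB k = 0.5, in percent of trials.

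| Spray mean | Medians tie | Median and both quartiles all tie | Nebulized mean not lower |
|---|---|---|---|
| 0.5 | 80 / 93 / 97 | 22 / 23 / 27 | 10 / 13 / 16 |
| 1.0 | 14 / 41 / 70 | 6 / 18 / 22 | 3 / 7 / 11 |
| 2.0 | 11 / 25 / 26 | 1 / 4 / 5 | <1 / 4 / 8 |
| 3.0 | 4 / 16 / 21 | <1 / 1 / 2 | <1 / 3 / 7 |

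With one device (24 v 12) the picture is similar: medians tie in 78–96% of trials at a mean of 0.5 and 18–65% at 1.0. Repeat runs agree to within about one point.

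**Step 3: what a ratio of means would deliver.** The approximate variance of the log ratio is 1/(n₁m₁) + 1/(n₂m₂), plus 1/(k·n) for each arm if overdispersed. The limits are 0.5 × exp(±1.96·SE). For a mean of 1 halved to 0.5:
- Poisson, 24 v 12: 1/24 + 1/6 = 0.208, SE 0.456, 95% CI about 0.20–1.22.
- Poisson, 24 v 24: 1/24 + 1/12 = 0.125, SE 0.354, 95% CI about 0.25–1.00.
- NB k = 1, 24 v 12: 0.208 + 1/24 + 1/12 = 0.333, SE 0.577, 95% CI about 0.16–1.55.

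The ratio gives direction and size, but with wide limits.

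**The case against.** A reader might infer that the plan compares arms by their medians and will therefore usually report no difference. The documents do not support that, for three reasons.

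First, sections 8.3 and 10.7 state no between-arm comparison, and they apply the median to continuous variables only. A count of 0, 1, 2 or 3+ could equally fall under the percentage rule, which would come close to a frequency table. This is an unresolved choice, not a declared scale.

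Second, the low rate is an inference. Section 7.1 allows for repeated opioid boluses against cough and has a contingency for cough that persists. Several episodes per patient are therefore foreseen, and at a Poisson mean of 3 the medians tie in only 4% of trials.

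Third, quartiles are planned too. Arms look identical on all three numbers in at most about 27% of trials in any scenario run for 24 v 24.

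All three stand, and they make the point conditional. They do not remove it. If the count is treated as continuous, its main summary is weak at low rates. If it is treated as categorical, no numeric summary is planned. The sponsor has stated no rate that would rule out the low end.

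It is also fair that the ratio of means will not settle the question at this size. Dispersion is poorly estimated from 12 patients, and coverage of the proposed interval was not simulated here.

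**Conclusion.** The point holds in conditional form. The primary variable is a count, the plan does not say how it will be summarised, and the only numeric summary on offer can conceal a halved rate when counts are low, at roughly one severe cough per spray patient or fewer. For 24 v 24, medians tie in about 80–97% of trials at a mean of 0.5, 14–70% at 1.0 and 4–21% at 3. Median and both quartiles all tie in about 22–27%, 6–22% and at most 2% respectively. In the same trials the mean count fails to favour the better arm in about 10–16%, 3–11% and at most 7%.

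All of this rests on assumed rates, a halving of the rate, Poisson or NB counts, and pooling of the two nebulizer arms, which the plan does not specify. It is worth correcting because the repair is cheap and supplies what section 2.3 needs for planning. It does not show that the trial will miss a difference.

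**What to change.** In sections 8.3 and 10.7, take the severe-cough count out of the median/IQR rule and name it as the primary variable. For each arm, report:
- the mean number of severe coughs per patient;
- the full frequency table (0, 1, 2, 3+);
- the percentage of patients with at least one severe cough.

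Then give the nebulized-to-spray ratio of mean counts with a 95% CI that allows for overdispersion, from a negative binomial model or a Poisson model with robust standard errors. Say in advance whether the two nebulizer arms are pooled for it.

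Add that the interval will be wide at 24/12/12, citing the Step 3 figures with their assumed rate. State that it estimates direction and size for planning the next trial and does not decide whether a difference exists. Median and IQR can stay for times and doses.

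The cost is a few sentences, with no new data, patients or procedures. The downside is that one heavy cougher can move the mean; the frequency table makes that visible.
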